8.3. Exploratory Pharmacokinetic Analyses

If data permits, PK data of metabolites will be analyzed in the similar way as for drug substance and similar output will be generated.

9. PHARMACOKINETIC (POPPK) ANALYSES

PopPK will be performed under a separate RAP and will be reported separately.

10. PHARMACODYNAMIC (AND / OR BIOMARKER) ANALYSES

10.1. Exploratory Pharmacodynamic and Biomarker Analyses

10.1.1. Endpoint / Variables

Following table describes the pharmacodynamic/biomarker end points:

Parameter	Parameter Description/Derivation	Part A	Part B
PGD2			X
PGE2			X
Creatinine #		X	X
tPGDM #		X	X
tPGEM #		X	X
6-keto-PGF1A			X
PGF2A			X
TXB2			X
Creatinine corrected data for tPGDM and tPGEM #	Three versions of data to be considered: 1.Raw data(mass) 2. Aggregated data 0-12hrs 3. Aggregated data 12-24hr 4. Aggregated data 24-48hrs Each version of data(mass) divided by time matched creatinine(mass)	X	X
Baseline corrected urinary tetranor data for tPGDM and tPGEM #	Post dose data divided by time matched baseline data Three versions of data to be considered: 1.Creatinine corrected raw data 2. Creatinine corrected aggregated data 0-12hrs 3. Creatinine corrected aggregated data 12-24hrs	X	X
Baseline corrected urinary tetranor data for creatinine #	Post dose data divided by time matched baseline data Three versions of data to be considered: 1.Raw data 2. Aggregated data 0-12hrs 3. Aggregated data 12-24hrs	X	X

Parameter	Parameter Description/Derivation	Part A	Part B
Placebo corrected data for tPGDM and tPGEM #	
Creatinine corrected data from active dose divided by time matched placebo data and then find ratio to baseline.
 
Three versions of data to be considered:
 
 1.Creatinine corrected raw data 2. Creatinine corrected aggregated data 0-12hrs 3. Creatinine corrected aggregated data 12-24hrs 	X	
Placebo corrected data for creatinine #	
Data from active dose divided by time matched placebo data and then find ratio to baseline.
 
Three versions of data to be considered:
 
 1.Raw data 2. Aggregated data 0-12hrs 3. Aggregated data 12-24hrs 	X	
Time matched PK Concentration for urinary tetranor data for tPGDM and tPGEM	
For each PD marker interval, use the upper bound as target time; e.g. for 0-2hr interval, 2hr is the target time
 
Identify PK concentration with nominal time at the target time;
 
If there is no PK sample taken at target time, use the PK concentration data with nominal time before but closest to target time;
 
Use 0 PK concentration for placebo
	X	X
Ratio of tPGDM/tPGEM #	
Time matched ratio for tPGDM/tPGEM
 
Three versions of data to be considered:
 
 1.Creatinine corrected raw data 2. Creatinine corrected aggregated data 0-12hrs 3. Creatinine corrected aggregated data 12-24hrs 4. Aggregated data 24-48hrs 	X	X

Urine tetranor and urine creatinine data should be considered as mass (Mass=Concentration*Volume).

Raw data – Mass data for each of the intervals 0-2, 2-4, 4-6, 6-8, 8-12 &12-24. (predose and postdose)

Aggregated data 0-12hrs - Add the mass from each interval till 12 hrs (predose and postdose)

Aggregated data 12-24hrs - Mass from 12-24hr interval (predose and postdose)

Aggregated data 124-48hrs - Mass from 24-48hr interval (postdose)

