Vital signs (pulse rate, blood pressure (bp), respiratory rate, and oral temperature)	X	X		←=====X=====→					(X)	X Vitals assessed at screening (triplicate measurements for pulse and (bp)) (and admission (single measurements). During treatment period vitals assessed predose (triplicate measurements for pulse and bp) and postdose (single measurements) every 15 min for 1 hr, hourly up to 6 hr, then at 12 hr, 24 hr, 36 hr, 48 hr, and 72 hr post-dose. See Section 8.2.2 for further information
Randomization				X						Randomization will occur before first dose in period 1.
Genetic sample				X						Any time predose on Day 1. This research may be described in a separate Informed Consent Form (ICF) or as part of a combined ICF. A separate signature is required where participant participation is optional
Study intervention				X						

Part A- Single Dose										
Procedure	Screening (up to 30 days before Day 1)	Treatment Period [Days] (for each dosing period)						E.D.	Follow-up (~14±1 days post last dose)	Notes E.D = early discontinuation/withdrawal
		-2	-1	1	2	3	4			
Telemetry				X						Telemetry performed starting 30 min (±10 min) pre-dose to 12 hr (±20 min) post-dose
Adverse Event (AE) review				←-----X-----→				(X)	X	
Serious Adverse Event (SAE) review	X	←-----X-----→						(X)	X	
Concomitant medication review	X	←-----X-----→						(X)	X	
24hr urine sampling for Pharmacodynamics (PD)			X ¹	X ²	X ³	X ³		(X)		¹ combined void for windows of 24-22 hr, 22-20 hr, 20-18 hr, 18-16 hr, 16-12 hr, and 12-0 hr predose. ² combined void for windows of 0-2 hr, 2-4 hr, 4-6 hr, 6-8 hr 8-12 hr, and 12-24 hr post-dose ³ combined void for 24 hr

Part A- Single Dose										
Procedure	Screening (up to 30 days before Day 1)	Treatment Period [Days] (for each dosing period)						E.D.	Follow-up (~14±1 days post last dose)	Notes E.D = early discontinuation/withdrawal
		-2	-1	1	2	3	4			
Blood sampling for Pharmacokinetics (PK)				←=====X=====→				(X)		Predose, 5min, 30min, 1 hr, 1.5 hr, 2 hr, 3 hr, 4 hr, 6 hr, 8 hr, 10 hr, 12 hr, 18 hr, 24 hr, 36 hr, and 48 hr, 60 hr, and 72 hr post-dose
24 hr Holter Monitoring				X						Predose through 24 hr post-dose
Discharge from Clinical Unit								X	(X)	

- The timing and number of planned study assessments, including safety, PK, PD/biomarker or other assessments may be altered during the course of the study based on newly available data (e.g., to obtain data closer to the time of peak plasma concentrations) to ensure appropriate monitoring.

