4.3. Justification for Dose

Dose selection of GSK3439171A for this FTIH study was based on NOAEL data in the most sensitive species, predicted PK of humans using the PK data from preclinical species, and a target therapeutic exposure based on the in-vitro H-PGDS recombinant enzyme assay, and in-vivo dose-response evaluation of GSK3439171A in wild-type (WT) eccentric damage and dystrophin deficient (mdx) mouse models.

The human PK parameters were calculated from preclinical mouse, rat, dog and monkey data. A range of human clearance and volume of distribution values were estimated by a variety of liver blood flow (LBF), allometric scaling, and Physiologically Based PK (PBPK) methods using GlaxoSmithKline software package PK Predictor Pro version 2.0.2.8, Excel and GastroPlus 9.0, respectively. Human bioavailability was estimated by averaging the oral bioavailability of mice, rat, dogs, and monkeys and estimated from LBF and single species scaling. Based on allometry and LBF, the predicted median human clearance was 10.8 mL/min/kg. The predicted median (range) human volume of distribution was 4.6 L/kg (3.2-6.0) and the predicted median (range) of half-life was 6.1 h (4-22). The human oral absorption rate was assumed to be 6.0 h⁻¹, based upon the average of the preclinical species (7.5 h⁻¹). The predicted oral bioavailability median (range) was 61% (39%-68%). A 100% bioavailability can be used as a conservative approach.

GSK3439171 was given orally to adult dogs for 6 weeks, and rats for 8 weeks starting dosing as juveniles on Postnatal Day (PND) 28 through maturity. Principal toxicities were a slight microscopic liver effect in the dog (inflammatory cell infiltrates in

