13.4. Appendix 4: Study Phases and Treatment Emergent Adverse Events

13.4.1. Study Phases

Assessments and events will be classified according to the time of occurrence relative to study treatment

Study Phase	Definition
Pre-Treatment	Date ≤ Study Treatment Start Date
On-Treatment	Study Treatment Start Date < Date ≤ Study Treatment Stop Date + 3 days
Post-Treatment	Date > Study Treatment Stop Date + 3 days

Note: Estimated half-life of GSK3439171 is approx. 13 hours. The maximum of (5 half-lives ~ 65 hours ~ 3days) and after the Study Treatment End Date, lag time have been considered to be 3 days to define the end of treatment phase.

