13.12.10. Pharmacodynamic (and / or Biomarker) Figures

Pharmacodynamic: Figures					
No.	Population	IDSL / Example Shell	Title	Programming Notes	Deliverable [Priority]
Urinary Tetrnor					
6.1.	PD	LB_PLOT1	Plot of Urinary Tetrnor and Urinary Creatinine vs Time by Dose– Part A	
PD parameters: tPGDM, tPGEM
 
End points #:
 
 1)Creatinine corrected raw data, 2)Creatinine corrected aggregated data 0-12hrs, 3)Creatinine corrected aggregated data 12-24hrs 4)Creatinine corrected aggregated data 24-48hrs Baseline corrected value, Placebo corrected value and ratio of tPGDM/tPGEM for first 3 versions of the data mentioned above 
PD parameters: Creatinine
 
End points #:
 
 1)Raw data, 2)Aggregated data 0-12hrs 3)Aggregated data 12-24hrs 4)Aggregated data 24-48hrs Baseline corrected value and Placebo corrected value for first 3 versions of the data mentioned above 
Note: X-axis values – actual midpoint of collection
	SAC

Pharmacodynamic: Figures					
No.	Population	IDSL / Example Shell	Title	Programming Notes	Deliverable [Priority]
6.2.	PD	LB_PLOT1	Plot of Urinary Tetranor and Urinary Creatinine vs Time by Dose– Part B	
PD parameters: tPGDM, tPGEM for Day 1, 7, 9, 10 &17.
 
End points #:
 
 1)Creatinine corrected raw data, 2)Creatinine corrected aggregated data 0-12hrs, 3)Creatinine corrected aggregated data 12-24hrs 4)Creatinine corrected aggregated data 24-48hrs Baseline corrected value for first 3 versions of the data mentioned above 
PD parameters: Creatinine for Day 1, 7, 9, 10 &17
 
End points #:
 
 1)Raw data, 2)Aggregated data 0-12hrs & 3)Aggregated data 12-24hrs 4)Aggregated data 24-48hrs Baseline corrected value for first 3 versions of the data mentioned above 
Note1: X-axis values – actual midpoint of collection
 
Note2: Panel plot each day as panel. Data available on day 1 for all cohorts, day 7 & 10 for cohort 3 only, day 9 &17 for cohort 1&2.
	SAC

Pharmacodynamic: Figures					
No.	Population	IDSL / Example Shell	Title	Programming Notes	Deliverable [Priority]

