6.7.	PD	LIVER14	Plot of Urinary Tetrakor and Urinary Creatinine vs PK Concentration by Dose– Part A	
PD parameters: tPGDM and tPGEM
 
End points #:
 
 • Creatinine corrected raw data • Baseline corrected value and Placebo corrected value for creatinine corrected raw data 
PD parameters Creatinine
 
End points #:
 
 • Raw data • Baseline corrected value and Placebo corrected value for raw data 
Note: X-Axis- PD concentration & Y- Axis – PK concentration
 
Different colour for each subject
 
Note: For each PD marker interval, use the upper bound as target time; e.g. for 0-2hr interval, 2hr is the target time;
 
Identify PK concentration with nominal time at the target time; If there is no PK sample taken at target time, use the PK concentration data with nominal time before but closest to target time;
 
Use 0 PK concentration for placebo
	SAC

Pharmacodynamic: Figures					
No.	Population	IDSL / Example Shell	Title	Programming Notes	Deliverable [Priority]
6.8.	PD	LIVER14	Plot of Urinary Tetranor and Urinary Creatinine vs PK Concentration by Dose– Part B	
PD parameters: tPGDM and Tpgem for Day 1, 10 &17
 
End points #:
 
 • Creatinine corrected raw data • Baseline corrected value for creatinine corrected raw data 
PD parameter: Creatinine for Day 1, 10 &17
 
End points #:
 
 • Raw data • Baseline corrected value for raw data 
Note: : X-Axis- PD concentration &Y- Axis – PK concentration . Panel plot with each day in separate panel and each subject different symbol. Data available on day 1 for all cohorts, day 10 for cohort 3 only, day 17 for cohort 1&2.
 
Note: For each PD marker interval, use the upper bound as target time; e.g. for 0-2hr interval, 2hr is the target time;
 
Identify PK concentration with nominal time at the target time;If there is no PK sample taken at target time, use the PK concentration data with nominal time before but closest to target time;
 
Use 0 PK concentration for placebo
	SAC

Pharmacodynamic: Figures					
No.	Population	IDSL / Example Shell	Title	Programming Notes	Deliverable [Priority]

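### Pairing each urine PD interval with the plasma concentration at its end understates 12-24 h exposure by about 29% in the exploratory concentration-effect plots

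*SAP*

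**What the plan says.** The endpoint table in SAP 10.1.1 defines a time-matched PK concentration for the urinary tetranor data: "For each PD marker interval, use the upper bound as target time; e.g. for 0-2hr interval, 2hr is the target time". It adds a fallback: "If there is no PK sample taken at target time, use the PK concentration data with nominal time before but closest to target time". Placebo is assigned a concentration of zero.

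The footnote to that table defines the PD quantity: "Raw data – Mass data for each of the intervals 0-2, 2-4, 4-6, 6-8, 8-12 &12-24". It is concentration multiplied by urine volume, so it is a total over the collection window and not a value at one time.

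SAP 13.12.10 applies the rule to Figures 6.7 to 6.10 (Parts A and B, by dose and by subject), again saying "use the upper bound as target time; e.g. for 0-2hr interval, 2hr is the target time". In these figures PD is on the x-axis and plasma concentration on the y-axis. The interval data are plotted for tPGDM, tPGEM and creatinine, with the windows together. The SAP gives no reason for choosing the end of the interval. Some of its plots of the same urine data against time, such as Figures 6.1 and 6.2, use "X-axis values – actual midpoint of collection".

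**The concern.** Urine collected from 12 to 24 h contains metabolite produced throughout those twelve hours. The concentration at 24 h describes only the last moment of the window and, while concentrations fall, it is the lowest value in it. The longer the window relative to the half-life, the larger the gap. The windows run from 2 to 12 hours, so the gap is not the same for each.

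If the error were one constant factor, the plots would merely be rescaled. Because it differs by window, points from the same participant are moved by different amounts. The 12-24 h points are moved most, towards too low a concentration for the observed effect. These four figures are the only displays of PD effect against plasma concentration in this SAP, and protocol 2.1 says the study is meant to inform doses for later studies.

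**Working it through.** The documents give no figure for this error, so there is none to reproduce.

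**Inputs**
- Windows: 0-2, 2-4, 4-6, 6-8, 8-12 and 12-24 h (SAP 10.1.1).
- Half-life: "Estimated half-life of GSK3439171 is approx. 13 hours" (SAP 13.4.1). The preclinical prediction in protocol 4.3 was 6.1 h, range 4 to 22 h.
- Absorption rate constant ka: 6.0/h (protocol 4.3). The documents give no other value; 1.5/h and 1.0/h below are assumptions.
- Time of peak: about 2 h (ECG note, Part B schedule, protocol 1.3).
- Plasma samples: every window boundary, with further samples inside the first and the longer windows, including "8 hr, 10 hr, 12 hr, 18 hr, 24 hr, 36 hr, and 48 hr" (protocol 1.3, Part A). The profile days in Part B have the same times.

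**Windows in the declining phase.** Let k = ln 2 / half-life and x = k × window length. For mono-exponential decline, end concentration / interval average = x / (e^x − 1).

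At 13 h, k = 0.0533/h:
- 12-24 h: x = 0.640, e^x = 1.896, ratio 0.640/0.896 = 0.714, or −28.6%.
- 8-12 h: x = 0.213, e^x = 1.238, ratio 0.897, or −10.3%.
- 2-4, 4-6 and 6-8 h: x = 0.107, e^x = 1.113, ratio 0.948, or −5.2% each.

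At 6.1 h the same formula gives 0.469 (−53.1%), 0.790 (−21.0%) and 0.891 (−10.9%). Over the predicted range of 4 to 22 h, the 12-24 h error runs from −70.3% to −17.7%.

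**0-2 h window.** One-compartment oral model, single dose: C(t) proportional to e^(−kt) − e^(−ka·t). At a half-life of 13 h:

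| ka (/h) | Time of peak (h) | C(2 h) / average over 0-2 h |
|---|---|---|
| 6.0 (protocol) | 0.8 | 1.04 |
| 1.5 (assumed) | 2.3 | 1.34 |
| 1.0 (assumed) | 3.1 | 1.48 |

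A peak near 2 h suggests slower absorption than 6.0/h, but the documents do not settle the value.

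**Effect on the plot, as an illustration.** Assume direct inhibition with the protocol's IC50 of 7.77 ng/mL, and 12 h concentrations of 1 to 100 ng/mL falling with a 13 h half-life. Average inhibition over 12-24 h paired with the 24 h concentration lies on a curve with an apparent IC50 of about 5.6-5.7 ng/mL. Paired with the interval average, it lies at about 7.8-8.0 ng/mL.

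**Can the average be computed?** With 12, 18 and 24 h samples, the log-down trapezoid recovers the average exactly under mono-exponential decline. Under twice-daily dosing a second dose follows the 12 h sample and only 18 and 24 h come after it. With a 13 h half-life and ka from 1.0 to 6.0/h, on the first day or at steady state, the trapezoid then recovers about 79-89% of the true average. The end value gives about 72-77%.

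**The case against.** The strongest case on the other side is about scope. The rule belongs to an exploratory section and feeds four scatter plots. The PD mixed models in SAP 10.1.4.1 use dose, timepoint and their interaction, not concentration. SAP 11 places population PK/PD analysis in a separate plan. This stands, and it limits the point to those plots.

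Several stronger readings are tempting but not supported:
- **A 30-50% error.** The upper end needs the preclinical 6.1 h half-life. The SAP now works with about 13 h, and the protocol's amendment history says observed PK differed from the predictions.
- **A certain change of sign with false hysteresis.** At the protocol's ka the 0-2 h error is only +4%. The large overstatement needs an absorption rate that the documents do not state.
- **A biased potency estimate.** No IC50 is to be estimated from these figures; the apparent IC50 above only shows the direction of the shift.
- **The 12-24 h data lie near the IC50.** That depends on dose. Scaling the simulated peak of 0.24 µg/mL at 100 mg (protocol Table 2) to 180 mg gives 432 ng/mL. Ten and 22 hours after a 2 h peak, at a 13 h half-life, this is about 253 and 134 ng/mL, far above 7.77.
- **An inconsistency with the midpoint time plots.** Placing a collection on a time axis and choosing its paired concentration are different tasks, so this is a contrast and not a contradiction.

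Two defences of the end value are weaker. Trough concentration does matter for a target of staying above the IC50, but accumulated urine mass does not measure inhibition at trough. A delay between plasma and urine would make the relevant exposure earlier than the window, not later; the documents give no figure for it.

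Finally, within one window and under linear PK the error is close to a constant factor, so ordering by dose or participant survives. That is correct; the distortion arises where windows are plotted together.

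**Conclusion.** The concern holds for the exploratory concentration-effect plots and no further. At the SAP's half-life, end-of-interval pairing understates mean exposure by about 29% in 12-24 h, about 10% in 8-12 h and about 5% in each window between 2 and 8 h. In 0-2 h it overstates exposure by about 4% at the protocol's absorption rate, and by up to about 48% at an assumed 1.0/h. The 53% figure for 12-24 h applies only at the superseded prediction of 6.1 h.

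These sizes assume mono-exponential decline, with one-compartment absorption for the first window, and no delay between plasma drug and urinary metabolite. The unequal errors, not any single one, distort the pooled plots. The change is worth making because it is cheap; no model-based result in this SAP depends on it.

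**What to change.** In SAP 10.1.1 and in the notes to Figures 6.7 to 6.10, replace the upper-bound rule with: *the matched exposure for each PD interval is the time-averaged plasma concentration, AUC(t1-t2)/(t2-t1), calculated by the linear-up/log-down rule of Table 2.* Apply it on the full-profile days these figures use: each dosing period in Part A, and Days 1, 10 (cohort 3) and 17 (cohorts 1 and 2) in Part B.

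- Keep zero for placebo.
- Replace the nearest-earlier-sample fallback: if a boundary sample is missing, obtain the partial AUC by interpolation from adjacent samples; if that is not possible, set the value to missing.
- For any cohort dosed twice daily, footnote that the 12-24 h average is approximate, because only 18 and 24 h are sampled after the second dose.

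The cost is SAP wording and a few extra partial AUCs from the existing non-compartmental run. No new samples are needed. The remaining weakness is the approximation under twice-daily dosing.

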10.1.1.1. Drug Concentration Measures

Refer to [Appendix 5](#): Data Display Standards & Handling Conventions

10.1.2. Summary Measure

Refer to [Appendix 5](#): Data Display Standards & Handling Conventions (Section 13.5.3. Reporting Standards for Pharmacokinetic)

10.1.3. Population of Interest

The exploratory pharmacodynamics (and / or biomarker) analyses will be based on the PD population, unless otherwise specified.

10.1.4. Statistical Analyses / Methods

Details of the planned displays are provided in [Appendix 12](#): List of Data Displays and will be based on GSK Data Standards and statistical principles.

Unless otherwise specified, endpoints / variables will be summarised using descriptive statistics, graphically presented (where appropriate) and listed.

10.1.4.1. Statistical Methodology Specification

10.1.4.1.1. Statistical Methodology Specification for Part A (Single Dose)

Pharmacodynamic Statistical Analyses – Mixed Effect Model – Single Dose (Part A)
Endpoint / Variables
tPGDM, tPGEM, Creatinine, Creatinine corrected tPGDM and Creatinine corrected tPGEM (Aggregated values for predose 24-12hr & 12-0hr and postdose 0-12 hr, 12-24 hr & 24-48 hr)
Model Specification

Log_e transformed values of the endpoints will be statistically analyzed using Mixed Model (MM).
 
 • Fixed effect: dose, timepoint, dose*timepoint • Random effect: Subject 
An unstructured covariance structure for the G matrix will be used.
 
 • If this model fails to converge, alternative covariance structures may be considered. • Akaike’s Information Criteria (AIC) will be used to assist with the selection of covariance structure. 
Analyses will be done with the MIXED Procedure in SAS, using the Kenward-Roger option to estimate denominator degrees of freedom and standard errors

Model Checking & Diagnostics

 • For the Mixed Model, model assumptions will be checked, and appropriate adjustments may be applied based on the data. • Distributional assumptions underlying the model used for analysis will be examined by obtaining a normal probability plot of the residuals and a plot of the residuals versus the fitted

Pharmacodynamic Statistical Analyses – Mixed Effect Model – Single Dose (Part A)
values (i.e. checking the normality assumption and constant variance assumption of the model respectively) to gain confidence that the model assumptions are reasonable.

 • If there are any departures from the distributional assumptions, alternative transformations, such as data squared or square root of data, will be explored. • Non-parametric analyses will be conducted if the normality assumption does not hold.
Model Results Presentation
LS Geometric means and 90% CI are estimated for each dose as well as the estimate (90% CI) of change from baseline for each timepoint, using the time matched baseline.
Note: For post dose 24-48hrs baseline (predose) is not available

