4. STUDY DESIGN

4.1. Overall Design

This is a three-part study (Parts A, B and C). Part A will be a double-blind (sponsor unblinded), single oral dose, dose-rising, placebo-controlled, randomized (with respect to placebo allocation), 3 period crossover study in approximately 3 cohorts of participants. Part B will be double-blind (sponsor unblinded), up to 14 day repeat oral dosing, placebo-controlled, randomized (with respect to placebo allocation), dose escalation study with at least three dose levels in 3 separate cohorts of participants who were not enrolled into Parts A or C of this study. Part C will be an unblinded, randomized, crossover study where a single dose will be administered fasted or fed conducted in a separate cohort of participants than those who were enrolled in Parts A or B.

The starting dose for Part A will be 5 mg (see Section 4.3.3).

Part A: Single Ascending Dose

Each participant will participate in 3 dosing periods and will receive 2 doses of GSK3439171A and 1 dose of placebo in a randomized fashion. There will be an approximately 7 day (or 5 half-lives, whichever is longer) washout period between dosing in each session.

Approximately 9 participants will be enrolled in each cohort. Participants will be admitted to the clinical unit on Day -2 and will remain in the unit until completion of assessments on Day 4 as outlined in the SoA. Participants will be discharged from clinical unit for the washout period between dosing sessions and will return approximately 14 days after dosing in their last dosing session for a follow-up visit. Participants will be randomized to treatment sequences such that in each period up to 6 participants will receive active dose and up to 3 participants will receive placebo. A minimum of three cohorts is anticipated. If a participant is withdrawn from the study, the participant may be replaced as necessary with another participant assigned to the same treatment sequence with respect to active and placebo doses to ensure that at least 4 participants receive each active dose and 1 participant receives a placebo, and that these participants complete safety and PK assessments through at least 72hr post-dose (or 5 half-lives, whichever is longer). Additional participants may be dosed at a given level if additional data are necessary to establish safety, tolerability or PK parameters prior to dose escalation.

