10.1.4.1.2. Statistical Methodology Specification for Part B (Repeat Dose)

Pharmacodynamic Statistical Analyses – Mixed Effect Model – Repeat Dose (Part B)
Endpoint / Variables
tPGDM, tPGEM, Creatinine, Creatinine corrected tPGDM and Creatinine corrected tPGEM (Aggregated values for predose 24-12hr & 12-0hr and postdose 0-12 hr, 12-24 hr & 24-48 hr)
Model Specification
Log _e transformed values of the endpoints will be statistically analyzed using Mixed Model (MM).

 • Fixed effect: timepoint, dose, timepoint*dose • Random effect: Subject
An unstructured covariance structure for the G matrix will be used.

 • If this model fails to converge, alternative covariance structures may be considered. • Akaike’s Information Criteria (AIC) will be used to assist with the selection of covariance structure.
Analyses will be done with the MIXED Procedure in SAS, using the Kenward-Roger option to estimate denominator degrees of freedom and standard errors
Model Checking & Diagnostics

 • For the Mixed Model, model assumptions will be checked, and appropriate adjustments may be applied based on the data. • Distributional assumptions underlying the model used for analysis will be examined by obtaining a normal probability plot of the residuals and a plot of the residuals versus the fitted values (i.e. checking the normality assumption and constant variance assumption of the model respectively) to gain confidence that the model assumptions are reasonable. • If there are any departures from the distributional assumptions, alternative transformations, such as data squared or square root of data, will be explored. • Non-parametric analyses will be conducted if the normality assumption does not hold.
Model Results Presentation
LS Geometric means and 90% CI are estimated for each dose as well as the estimate (90% CI) of change from baseline for each timepoint, using the time matched baseline.
Note: For post dose 24-48hrs baseline (predose) is not available
Consider Day -1(predose), Day1, Day 7, Day 10, Day 17

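### The Part A urinary PD model has no subject-by-period term, so any period-to-period variance makes its change-from-baseline intervals too wide and its dose-by-timepoint intervals slightly too narrow

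*SAP*

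**What the plan says.** The Part A PD model in SAP 10.1.4.1.1 has "Fixed effect: dose, timepoint, dose*timepoint" and "Random effect: Subject". The endpoints are logged and enter as "Aggregated values for predose 24-12hr & 12-0hr and postdose 0-12 hr, 12-24 hr & 24-48 hr", which makes five values per period. Protocol 4.1 states that "Each participant will participate in 3 dosing periods and will receive 2 doses of GSK3439171A and 1 dose of placebo". Participants leave the unit between periods for a washout of about 7 days or longer.

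The baseline is specific to the period (SAP 13.6.1) and time-matched within it (SAP 5.2).

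On covariance, the section says "An unstructured covariance structure for the G matrix will be used", and then "If this model fails to converge, alternative covariance structures may be considered", with AIC as an aid to selection and Kenward-Roger for standard errors and degrees of freedom. It reports LS geometric means and change from time-matched baseline, both with 90% CIs. Shell PD_T1 (SAP 13.13) sets these out by dose and timepoint. The 24-48 hr window has no baseline and so no change.

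**The concern.** Urine collected before and after a dose in one admission shares that admission's conditions. It is likely to be more alike than urine from the same person in another admission. A single subject intercept treats all 15 values from a participant as equally correlated, so variation between a participant's periods is split between the subject variance and the residual.

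The quantity of most interest, change from the same-period baseline, is free of that variation, yet its CI is built from a residual that contains it. About six participants receive each active dose, so the period-specific baseline is the main source of precision, and the model would discard part of it. The dose-by-timepoint means err slightly the other way, because the model overstates how much a participant's other periods say about the current one.

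**Working it through.** The documents state no precision figure for this analysis, so there is none to reproduce.

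**Inputs from the documents.** There are five windows (SAP 10.1.4.1.1) and three periods (Protocol 4.1), so 5 × 3 = 15 values per participant. Each active dose goes to 6 participants (Protocol 1.2). SAP 5.1 lists six active doses. With three doses and nine participants per cohort (Protocol 6.3.1), that is two cohorts, or 18 participants. The protocol's three cohorts would be 27.

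**Inputs assumed.** Log-scale SDs are 0.40 for subject and 0.30 for residual. The ratio r of subject-by-period variance to residual variance is 0 to 2.

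**Does the stated covariance cover it?** An unstructured G matrix with one random intercept is a single variance. It holds no within-period correlation.

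**Algebra.** Write sp² for the subject-by-period variance and se² for the residual variance. Of the 14 within-subject degrees of freedom, 2 lie between periods and 12 within. The expected within-subject sum of squares is 2(se² + 5sp²) + 12se² = 14se² + 10sp². The subject-only residual therefore estimates about se² + (10/14)sp². The true variance of a mean within-period change at one dose is 2se²/6, with no sp². The SE inflation is about √(1 + 0.714r).

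**Simulation.** The AAP/APA/PAA crossover was simulated with 18 participants and five windows, 1,000 runs per setting. It was fitted by REML with Satterthwaite intervals in place of Kenward-Roger, at nominal 90%:

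| r | √(1 + 0.714r) | Simulated model SE / true SE, change | Coverage, change | Coverage, dose-by-timepoint mean |
|---|---|---|---|---|
| 0.25 | 1.09 | 1.10 | 93.5% | 88.5% |
| 0.5 | 1.16 | 1.16 | 93.4% | 87.5% |
| 1 | 1.31 | 1.26 | 97.0% | 86.0% |
| 2 | 1.56 | 1.52 | 98.4% | 84.6% |

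At r = 0, coverage was 88.5% to 90.7% for every contrast, so the model is sound under its own assumption. With 27 participants and r = 1, coverage for change was 96.3%.

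**Width at r = 1.** The mean fitted residual variance was 0.152, against a true 0.09 (the algebra gives 0.09 × 1.714 = 0.154). The SE of change is √(2 × 0.152/6) = 0.225 under the planned model and √(2 × 0.09/6) = 0.173 in truth. The simulated half-widths were 0.371 under the planned model and 0.286 with subject-by-period added. On the ratio scale, the limits are the estimate multiplied and divided by e^0.371 = 1.45, against e^0.286 = 1.33.

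**Why the means err the other way.** At r = 1 the fitted subject variance was 0.190, against a true 0.16. The fitted total (0.190 + 0.152 = 0.342) is close to the true total (0.16 + 0.09 + 0.09 = 0.34), but the correlation between periods is overstated: 0.190/0.342 = 0.56, against 0.16/0.34 = 0.47. Placebo-by-timepoint means, to which every participant contributes, kept 89.9% coverage.

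**With subject-by-period added.** Coverage was 87.6% to 92.5% across all contrasts and settings. For the dose-by-timepoint mean it was 88.5% at r = 1 and 89.0% at r = 2. The shortfall under the planned model is therefore small: 2.5 points (88.5 − 86.0) and 4.4 points (89.0 − 84.6).

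**The case against.** Several points for the plan have weight. The endpoints are exploratory, no hypothesis is tested, and no decision threshold is tied to these CIs. The larger error is conservative: overwide intervals for change cannot create a false signal of target engagement. SAP 10.1.1 also derives each participant's post-dose to baseline ratio, and Figure 6.5 plots geometric means of it with 95% CIs. Period variation cancels in those ratios, so a partial cross-check exists. All of this stands and keeps the point small.

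The SAP also has some latitude: "model assumptions will be checked, and appropriate adjustments may be applied based on the data". That clause names no term. The listed diagnostics look at normality and constant variance, not at clustering within a period. Other covariance structures are tied to non-convergence, which this simple model would not normally show. Kenward-Roger works within the assumed covariance and cannot restore a missing component.

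A reader might go further in two ways that the documents do not support:

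- **Dose versus placebo.** One might infer that this model's dose-placebo intervals are too narrow. SAP 5.1 lists such a comparison as a display descriptor, but neither the results presentation in SAP 10.1.4.1.1 nor shell PD_T1 contains it.
- **Part B.** With "Fixed effect: timepoint, dose, timepoint*dose" and subject alone as random (SAP 10.1.4.1.2), Part B might seem to have the same fault by day. Its only PD baseline is Day -1 (SAP 5.2), so each change is between days and day variance does not cancel. A simulation with four arms of nine, three or four days and ratios of 0.5 to 2 gave SEs at most about 7% too small and coverage of 87% to 89%. Those intervals would be slightly too narrow, not too wide.

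**Conclusion.** The point holds for Part A, conditionally. If subject-by-period variance is 0.5 to 2 times the residual variance, the SE of change from baseline is inflated about 1.15 to 1.55 times, and the dose-by-timepoint means cover about 85% to 88% instead of 90%. If that variance is zero, nothing is wrong. The documents give no estimate of it, so it would be too strong to say that the planned intervals are wrong as they stand.

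The results presentation speaks of means for each dose, and a reader might take that as an average over timepoints. Such averages would fare worse (coverage 82.1%, 75.1% and 71.0% at ratios 0.5, 1 and 2). PD_T1 shows means by timepoint, however, so those figures do not describe the planned output.

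The sizes rest on the assumed variances and on Satterthwaite degrees of freedom. The direction and rough size for change also follow from the algebra.

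**What to change.** In SAP 10.1.4.1.1, add a random subject-by-period effect beside the random subject effect, and state that it is dropped only if its variance is estimated at zero. Part B needs no change on this account.

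The cost is one line in the SAP and one further RANDOM term in the SAS code. No data collection or display changes. If the variance is zero, the added term costs essentially nothing. If it is not, the planned 90% CIs return to about nominal.
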